10.8.2 Clinical Laboratory Parameters

Serum chemistry and hematology data will be summarized by treatment group and visit. Descriptive statistics will be presented at each visit by treatment group for the parameters listed below. Shift tables of the baseline value compared to each post baseline value will be presented for the following selected laboratory parameters: a) alanine aminotransferase (ALT), aspartate aminotransferase (AST), blood urea nitrogen (BUN), creatinine, direct bilirubin, glucose, and cholesterol for chemistry; and b) hemoglobin, hematocrit, white blood cell (WBC) count, neutrophil count, lymphocyte count, and platelet count for hematology. Urinalysis data and pregnancy data will be listed only. In addition, all serum chemistry, hematology and urinalysis data outside the central laboratory standard reference ranges will be listed by parameter and treatment group.

Individual subject listings of clinical laboratory parameters at each visit will be provided. Values for any serum chemistry, hematology, and urinalysis values outside the central laboratory reference ranges will be flagged on the individual subject data listings.

The following laboratory safety assessments will be included in the subject listings:

- Hematology: complete blood count (CBC) with differential and platelet counts. CBC includes red blood cells (RBCs), WBCs, hemoglobin, hematocrit, mean corpuscular volume (MCV), mean corpuscular hemoglobin (MCH), and mean corpuscular hemoglobin concentration (MCHC)
- Serum chemistry: albumin, alkaline phosphatase, ALT, AST, BUN, calcium, chloride, bicarbonate (HCO_3), creatinine, direct bilirubin, gamma-glutamyl transpeptidase (GGT), glucose, lactate dehydrogenase (LDH), magnesium, phosphorus, potassium, sodium, total cholesterol, total protein, and uric acid
- Urinalysis: including determination of the presence of protein, glucose, ketones, occult blood, and WBCs by dipstick, with microscopic examination, if indicated

10.8.3 Vital Signs

Descriptive statistics will be used to summarize and present vital sign measurements at each nominal timepoint for each treatment group. Individual subject listings of vital signs at each timepoint will also be provided by treatment group.

10.8.4 Electrocardiogram (ECG)

The ECG data will be obtained directly from the 12-lead ECG traces. These data include the PR interval, QTcB interval, QRS duration, and heart rate. The ECG data will be listed by subject. Descriptive statistics will be used to summarize ECG measurements at each visit for each treatment group. In addition, a shift table of ECG interpretation results will be presented at each visit by treatment group. Individual subject listings of ECG parameters at each timepoint will also be provided by treatment group.

10.8.5 Physical Examination

Individual subject listings of physical examination results will be provided by treatment group.

10.8.6 Pulmonary Function Tests (PFT)

Under Protocol Version 1, for screening and baseline PFTs, 3 PFTs will be performed on separate days during the screening period (within 5 weeks prior to dosing). The first of these tests will be performed before and after bronchodilator administration to determine if the subject qualifies for the study, whereas the other 2 will be averaged to serve as the subject's baseline value.

Under Protocol Version 2 and later, for screening and baseline PFTs, 2 PFTs will be performed on separate days during the screening period (within 5 weeks prior to dosing). The first of these tests will be performed before and after bronchodilator administration to determine if the subject qualifies for the study, whereas the other PFT (performed without bronchodilator administration) will serve as the subject's baseline value. If the baseline PFT does not meet quality criteria, the pre-bronchodilator screening PFT (or repeat pre-bronchodilator screening PFT, if appropriate) will be substituted as the baseline value.

PFT parameters include:

FVC: forced (expiratory) vital capacity

FEV₁: forced expiratory volume over one second

TLC: total lung capacity

DLco/Hb:carbon monoxide diffusion capacity, corrected for hemoglobin

RV: residual volume

The assessment of changes in lung function during this study will be performed by comparing the subject's follow-up PFT parameters (i.e., Visit 9 Day 29-MD and Visit 16 Day 8-FU visits) to

their baseline value. Each subject's percent change from baseline will be calculated by subtracting the individual subject's baseline value from the value at the desired time point and then dividing this calculated value by the individual subject's baseline value and multiplying by 100. The individual subject's percent change from the baseline value will be used to calculate the mean percent change from baseline for the treatment group using a SAS procedure such as Proc Univariate.

The following decreases in PFT parameters have been prospectively defined as significant and may be clinically important: TLC $\geq 8\%$, FEV₁ $\geq 12\%$, FVC $\geq 12\%$, and/or DLco/Hb $\geq 15\%$ change from the baseline value. PFTs demonstrating a potentially clinically significant decline from baseline must be confirmed by repeating the abnormal parameter. A confirmed decline in a PFT parameter will be reported as an adverse event and will be used for analysis purposes.

Listings of individual subject data by study visit and treatment assignment will be provided for each of the PFT parameters as well as the percent change from baseline. Summary statistics of the PFT parameters will be provided by treatment group for the actual PFT value and the percent predicted for each of the PFT parameters specified above (reference populations are NHANES III for Spirometry and Crapo 1982 for DL_{co}/Hb^{3,4}).

10.8.7 Bronchoalveolar Lavage (BAL) MMP-12

A BAL will be performed during the screening period and after receiving the last dose of study medication (i.e., from Visit 14 Day 3-FU to Visit 16 Day 8-FU). Analysis of the BAL macrophage MMP-12 mRNA levels (which are increased when macrophages are activated) will be measured.

Subject listings of the screening and Visit 16 Day 8-FU MMP-12 levels, as well as the % change from screening, will be provided. Summary statistics of the relative expression of MMP-12 levels at screening and following the last dose of study medication, as well as the percent change from Screening, will also be provided for each treatment group.

10.8.8 High Resolution Computed Tomography (HRCT)

The diagnostic criteria for IPF in study 203PF201 are based on the recently updated evidence-based guidelines developed by the ATS/ERS/JRS/ALAT joint task force for the diagnosis and management of IPF⁵. An HRCT scan will be performed during screening to establish subject eligibility as well as the pre-dosing pattern and extent of disease. Each subject will have a repeat HRCT performed within 21 days after receiving the last dose of study medication to assess for changes in the extent of IPF. The details of the independent HRCT and surgical lung biopsy (SLB) assessments are described in the Perceptive Informatics 'Independent Review Manual'.

For the eligibility review, a minimum of 2 and a maximum of 3 independent radiologists will evaluate the screening HRCT images to determine whether they fulfill the radiographic criteria for UIP pattern. If a SLB is available at screening (lung biopsy performed prior to screening is acceptable), a minimum of 2 and a maximum of 3 independent pathologists will assess the SLB for UIP pattern. For all subjects that have a SLB available at the time of screening, the combined results of radiology and pathology assessments will be used to determine subject eligibility. If a

subject does not have a SLB available at the time of screening, eligibility will be determined by radiology assessment alone. A consensus panel will be convened if subject eligibility is not clear based upon the initial independent review of the HRCT and SLB.

For the safety review, the independent radiologists will also compare each subject's screening and follow-up HRCT images to determine whether a change in IPF by HRCT has occurred. A *qualitative* and *semi-quantitative* assessment will be performed. The *qualitative* assessment will summarize the change in the combination of honeycombing and reticulation (i.e., same, better, much better, worse, much worse, unknown). For the *semi-quantitative* assessment, the extent of fibrosis including the extent of reticular abnormalities and honeycombing together will be scored for each lung separately as well as for both lungs combined using the following categories: absent, 1-25%, 26-50%, 51-75%, 76-100%, or unknown. At the time of review the radiologists will also assess the HRCT images for technical adequacy and quality (i.e., noting anatomy that is not complete, motion artifacts present, crucial anatomy is out of the field of view, other, etc.).

Shift tables of the semi-quantitative HRCT assessments will be presented by treatment group. Individual subject listings of all HRCT and SLB eligibility assessments, as well as the qualitative and semi-quantitative HRCT safety assessments, will also be provided (including reviewer comments and consensus panel assessments).

10.8.9 Pulse Oximetry

Descriptive statistics will be used to summarize and present O₂ saturation at each visit, and change from baseline, for each treatment group. Individual subject listings of O₂ saturation at each visit will be provided.

10.8.10 Immunogenicity (Anti-BG00011 Antibodies)

Blood samples for potential antibodies to BG00011 will be collected during screening and prior to dosing on Visit 2 Day 1-MD. Post-dose samples will be obtained on Visit 19 Day 29-FU and Visit 85 Day 85-FU.

Each blood sample will initially be tested for the presence of anti-BG00011 antibodies using a validated electrochemiluminescence (ECL) method. Confirmed positive samples using the screening assay will be titered and subsequently tested using a validated neutralization assay.

Antibody results will be presented by treatment group and subject in listings. The incidence of antibodies to BG00011 (both binding as well as neutralizing) will be tabulated over time by treatment group using descriptive statistics. The antibody titer and natural log transformed results will be summarized and presented using descriptive statistics. If antibodies are present, their effect on PK parameters will be explored.

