6. STUDY DESIGN

This is a multi-center, randomized, double-blind, placebo-controlled, multiple dose, dose-escalation study designed to evaluate the safety, tolerability, PK, immunogenicity, and impact on BAL and peripheral blood biomarkers of BG00011 activity in subjects with IPF conducted at approximately 15 centers in North America.

Approximately 40 subjects will be enrolled into 5 sequential ascending dose cohorts ([Table 1](#)). Cohorts will include 8 subjects randomized to receive either BG00011 (6 subjects) or placebo (2 subjects). Additional subjects may be enrolled if deemed appropriate by the Data Safety Monitoring Board (DSMB). Doses to be administered are as follows:

Table 1: Dosing Cohorts

Cohort	Dose	Number of Subjects	
		BG00011	Placebo
1	0.015 mg/kg	6	2
2	0.1 mg/kg	6	2
3	0.3 mg/kg	6	2
4	1.0 mg/kg	6	2
5	3.0 mg/kg	6	2
Total Number of Subjects		30	10

Subjects with clinical symptoms and features consistent with IPF prior to screening; forced vital capacity (FVC) \geq 50% of predicted value; carbon monoxide diffusion capacity, corrected for hemoglobin (DL_{CO}/Hb) \geq 30% of predicted value; oxygen (O₂) saturation $>$ 90% while breathing ambient air at rest or receiving \leq 2 L/minute of supplemental oxygen; residual volume (RV) \leq 120% of predicted value; a ratio of the forced expiratory volume in one second (FEV₁) to FVC \geq 0.65 after the use of a bronchodilator during screening pulmonary function tests (PFTs); high resolution computed tomography (HRCT) consistent with usual interstitial pneumonia (UIP) pattern; and who meet the other inclusion/exclusion (I/E) criteria are eligible to enroll in the study. Subjects who do not qualify for study eligibility may be rescreened at the discretion of the Principal Investigator.

Each subject within a dose cohort will be randomized to receive either BG00011 or placebo and will participate in 2 consecutive study periods: 1) each subject will receive 8 consecutive weekly doses of BG00011 (or placebo) (Period 1; Multiple Dose [MD] phase); and, 2) each subject will be monitored for 12 weeks (8 weeks for Cohorts 4 and 5) following administration of the last dose of study drug (Period 2; Follow-Up [FU] Phase).

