6.1 NOMENCLATURE FOR STUDY PERIODS AND STUDY DAYS

Days for the MD period are designated with an “MD” and days for the FU period are designated with an “FU.”

- Day 1-MD is the day the subject receives the first dose during the MD period of the study.
- Day 1-FU is first day of the follow-up period, which should coincide with the day of last dose during the MD period (Day 50-MD).

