7. TREATMENT

BG00011 will be administered as an SC injection. Doses will be 0.015 mg/kg, 0.1 mg/kg, 0.3 mg/kg, 1.0 mg/kg, and 3.0 mg/kg. Weight obtained at initial screening will be used to calculate dose throughout the study. At the end of a screening period, eligible subjects will return for dosing on Day 1-MD. Study drug will be administered once weekly for 8 doses (7 weeks), i.e., on Days 1-MD, 8-MD, 15-MD, 22-MD, 29-MD, 36-MD, 43-MD, and 50-MD of the multiple-dose period.

In cohorts 1 to 3, each subject’s participation in the study will be for approximately 24 weeks (~5.5 months), i.e., up to 5 weeks to perform screening/entry evaluations, followed by 7 weeks of double-blind study dosing (8 doses) and a Follow-up period of 12 weeks. For Cohorts 4 and 5, the subject’s participation in the study will be for approximately 23 weeks (~5.5 months), i.e., up to 8 weeks to perform screening/entry evaluations, followed by 7 weeks of double-blind study dosing (8 doses) and Follow-up period of 8 weeks.

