10.9 Data Safety Monitoring Board

An independent DSMB experienced in the oversight and monitoring of the conduct of clinical trials will determine whether dose escalation should proceed. The DSMB will be comprised of a biostatistician and two pulmonologists with expertise in interstitial lung diseases. The DSMB members' responsibilities and the process for data reviews and dose-escalation are described in the DSMB Charter.

Dose escalation will be based on the DSMB's review of unblinded PK and safety data through Day 15 from the initial 4 (of 8) subjects administered BG00011 or placebo (3:1, respectively) in each cohort. Safety assessments will include a review of AEs, vital signs, physical examination, clinical laboratory tests, and pulse oximetry from these visits. In order to allow for compilation and evaluation of the data, it is anticipated that the DSMB will convene approximately 9-10 weeks after the first 4 subjects in the previous cohort are initially dosed.

Serious adverse events will be provided to the DSMB on an ongoing basis throughout the study. Updated safety (including BAL, PFTs, and HRCT results) and PK information on all participants will be provided in each subsequent DSMB data package. For example, at the DSMB meetings for Cohorts 2 and 3, updated safety and PK data will be available through at least week 8 of the follow-up period (i.e., complete PK data through the dosing phase and follow-up BAL, PFT, and HRCT) for all participants in Cohorts 1 and 2, respectively.

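### The antibody incidence table by dose and visit has no category for a negative sample that still contains BG00011, and the listed Day 85-FU sample falls outside follow-up for the two highest doses

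*SAP*

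**What the plan says.** SAP Section 10.8.10 lists antibody samples at screening and before the first dose, and then: "Post-dose samples will be obtained on Visit 19 Day 29-FU and Visit 85 Day 85-FU". It draws no distinction between cohorts. On testing it says: "Each blood sample will initially be tested for the presence of anti-BG00011 antibodies using a validated electrochemiluminescence (ECL) method". Confirmed positives go on to titer and a neutralization assay. The summary is then: "The incidence of antibodies to BG00011 (both binding as well as neutralizing) will be tabulated over time by treatment group using descriptive statistics". If antibodies are found, their effect on PK parameters is to be explored. The section states no drug-tolerance limit and no rule for a negative result obtained with drug in the sample.

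On dose, Section 7 says: "Doses will be 0.015 mg/kg, 0.1 mg/kg, 0.3 mg/kg, 1.0 mg/kg, and 3.0 mg/kg". All cohorts receive eight weekly doses. Section 6.1 anchors the follow-up calendar to the last dose: "Day 1-FU is first day of the follow-up period, which should coincide with the day of last dose during the MD period (Day 50-MD").

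On length of follow-up, Section 6 says: "each subject will be monitored for 12 weeks (8 weeks for Cohorts 4 and 5) following administration of the last dose of study drug". Section 7 repeats the 8 weeks for Cohorts 4 and 5, and Section 10.8.11 places an assessment for those cohorts at Day 57-FU.

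**The concern.** Drug in a sample can reduce what an anti-drug antibody immunoassay detects. A negative result is therefore conclusive only if the drug concentration is below the level the assay tolerates. BG00011 is a humanized monoclonal antibody (Section 5), so some drug may still be present 28 days after the last of eight weekly doses, and more of it at higher doses. Any masking would then run along the comparison the table displays: incidence would look lower at the top doses for a reason unrelated to immunogenicity.

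Immunogenicity is a secondary objective. Section 13 drops the dose-trend test because of small samples, so this descriptive table is the SAP's only planned summary of antibody incidence across doses. Masked positives could also be taken for antibody-negative subjects in the exploration of antibody effect on PK.

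The sampling calendar adds to this. A late sample gives drug time to clear, but for the two highest doses the listed late sample comes after follow-up ends.

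**Working it through.** **1. The SAP's own figure.** Section 8 gives an 82% chance of observing an event among 6 treated subjects at a true rate of 25%. Check: 1 − 0.75^6 = 0.822. It reproduces.

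**2. Sampling times.** Day 1-FU is the day of the last dose (Section 6.1).
- Day 29-FU is 29 − 1 = 28 days after the last dose.
- Day 85-FU is 85 − 1 = 84 days, or 12 weeks, after it.
- Cohorts 4 and 5 are followed for 8 × 7 = 56 days, which ends at Day 57-FU.

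Cohorts 1 to 3 therefore have two listed post-dose antibody samples within follow-up. Cohorts 4 and 5 have one, Day 29-FU.

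**3. Drug remaining.** The SAP gives no half-life, so the values below are assumptions. Fraction of the last-dose level remaining = 2^(−t / half-life).

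| Assumed half-life | t = 28 days (Day 29-FU) | t = 84 days (Day 85-FU) |
|---|---|---|
| 7 days | 6.25% | 0.02% |
| 14 days | 25.0% | 1.6% |
| 21 days | 39.7% | 6.25% |

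With a 3-day half-life only 0.2% would remain at 28 days, so the concern weakens quickly if the drug clears fast.

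**4. Gradient across doses.** Dose ratio, top to bottom: 3.0 / 0.015 = 200. To turn this into a ratio of residual drug, sum the eight weekly doses at 28 days after the last: dose × Σ 2^(−(28 + 7i) / half-life), for i = 0 to 7. With dose-proportional PK and equal half-lives the sums cancel and the ratio is 200. Otherwise it moves:
- Exposure proportional to dose^b: 200^0.8 = 69; 200^1.2 = 577.
- Half-life 14 days at the low dose and 10 days at the high dose: 91.
- Half-life 7 days at the low dose and 21 days at the high dose: about 2,600.

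In all these scenarios the higher dose leaves more drug, but the size of the ratio is not known from the SAP.

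**5. What masking would do with 6 subjects.** Let m be the assumed share of true positives that read negative. At a true antibody rate of 25%, the chance of seeing at least one positive is 1 − (1 − 0.25(1 − m))^6.

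| m | Chance of at least one positive |
|---|---|
| 0 | 82.2% |
| 0.25 | 71.2% |
| 0.50 | 55.1% |
| 0.75 | 32.1% |
| 1 | 0% |

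The first row is the Section 8 figure. The others are illustrations, since m is not known.

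**6. Choice of denominator.** Dividing positives by positives plus conclusive negatives drops negatives with high drug levels but keeps positives with high drug levels. With 1 positive and 5 inconclusive, it reads 1/1 = 100%. With 0 positive and 6 inconclusive, it is 0/0. Over all sampled subjects the same data read 1 positive and 5 inconclusive of 6, and 0 positive and 6 inconclusive of 6.

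**The case against.** The strongest reply is that the point rests on silence. Section 10.8.10 never says that an assay-negative sample counts as antibody-negative, and it calls the ECL method validated. A tolerance rule could sit in the assay documentation, the TFL shells or the separate PK analysis plan, none of which is at hand. Masking depends on absolute concentration against tolerance, and neither is given. The table is descriptive, and by-subject listings accompany it.

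Much of this stands, and it limits the claim to a risk. It does not remove the point: the SAP keeps the incidence table in its own text, and the result categories and denominator of that table belong there.

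The SAP does not support some stronger readings that a reader might infer:
- That residual drug at Day 29-FU differs 200-fold between groups. Only the dose ratio is 200.
- That incidence at the top doses will be understated. This requires concentrations above a tolerance that is not stated.
- That immunogenicity by dose is itself the objective. Section 5 asks only for immunogenicity in subjects with IPF; the split by dose comes from the table.
- That the needed concentrations are known to exist. Section 10.9 says "updated safety and PK data will be available through at least week 8 of the follow-up period", but the sentence goes on to describe complete PK data through the dosing phase, and its example covers Cohorts 1 and 2. It does not establish a Day 29-FU concentration in Cohorts 4 and 5.
- That the PK exploration has a defined antibody-negative comparison group. It does not; that consequence is conditional too.

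**Conclusion.** The point holds as a conditional weakness in the incidence table together with a conflict in the sampling calendar. The conflict needs no outside assumption: Day 85-FU is 84 days after the last dose, while follow-up in Cohorts 4 and 5 is 56 days. On the listed schedule, the groups where residual drug is most plausible have only the earlier post-dose sample, so incidence over time is not comparable across doses.

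The masking risk rests on assumed half-lives, on exposure rising with dose, and on concentrations exceeding an unstated tolerance. If they do, the table would understate incidence at the top doses by an amount the SAP does not allow one to calculate. If they do not, the results are unchanged and the negatives are better supported. This is a worthwhile, inexpensive improvement, not a demonstrated error.

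**What to change.** In Section 10.8.10:
- Classify an antibody-negative sample as inconclusive when the concurrent BG00011 concentration, where available, exceeds the assay's validated drug tolerance. Cite the source of the tolerance value, and flag negatives with no concurrent concentration.
- Report counts of positive, conclusive negative and inconclusive over all sampled subjects, by dose group and visit, with the number sampled. Do not use positives over positives plus conclusive negatives as the incidence.
- In any exploration of antibody effect on PK, do not count inconclusive subjects as antibody-negative.
- Reconcile the antibody sampling days with the follow-up lengths in Sections 6 and 7, so that the table shows which visits apply to Cohorts 4 and 5.

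The cost is a few sentences, a small merge of antibody and concentration data, and probably fewer conclusive negatives at the high doses.
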